6.4.2. Maintenance of randomization codes and procedures for breaking code

Patients' GP and usual care team will be aware of their group allocation and treatments, and any medical emergency can be managed without the need to break any code. The investigators will be informed of the suspected unexpected serious adverse event (SAE) related to the study intervention. In this instance, the patient's GP or practice nurse will inform the CI. The CI will inform the Sponsor within 7 days of becoming aware of this. Even if the trial treatments are discontinued, the study participants will be requested to attend for continued follow-up and assessment.

Unblinding will not be part of managing an SAE as participants in both arms can be commenced on ULT and flare prophylaxis. If accidental unblinding occurs as part of managing

Page 30 of 71 Treat to target in gout Protocol Final Version 1.1 date 29 May 2019

an SAE, it will be reported to the Sponsor with the SAE, however, in cases where accidental un-blinding was not associated with an SAE, such actions will also be reported to the Sponsor immediately as practicable by phone or fax, followed by a written narrative of the event within 48 hours.

Planned interim analysis will occur at the end of the internal pilot. The results of the interim analysis at this time-point will be available to the trial management group (TMG), TSC, and DMC. For monitoring purposes, the TMG and TSC will monitor patterns of SAEs across the blinded treatment groups. The DMC will review unblinded safety data and will report their assessment of whether there are any safety concerns to the TSC chair.

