6.4 RANDOMIZATION AND BLINDING

6.4.1 Randomization and blinding

Randomization will be in a 1:1 ratio, stratified by region, contraindication to or intolerance of colchicine prescription intolerance, using random permuted blocks of 2 to 6. Ten randomization lists will be prepared by the study statistician and stored on a secure server in Keele CTU, to which no members of the trial team will have access. One of these lists will be randomly selected by the database manager for use in the trial.

The trial management group and the TSC will be blind to group allocation; none of these individuals will have contact with study participants. The statistician will not be blind to group allocation, owing to differences in serum urate that will be apparent. Unblinded data will be made available to the DMC where appropriate. In such an event, the statistician will prepare the relevant data summaries and the identity of the treatment groups. Unblinding to the study team will only occur once the main trial analyses have been completed.

Randomization will be during office hours using a secure centralised web-based, automated computer generated randomization system provided by the Keele University Clinical Trials Unit (CTU). Authorised personnel at the trial site will be allocated personalised log in details by Keele CTU, in order to access the randomization system. Alternatively, the research or practice nurse can call Keele CTU and the CTU will perform the randomization on the site's behalf. Authorized staff at the CTU will access the randomization tool to perform randomization and inform the nurse of the allocation. The participants' GP and usual care team will be informed of the participants' allocation verbally and in writing within two working days.

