- If serum urate is ≥360 µmol/L despite maximum licensed dose of allopurinol or febuxostat, uricosuric drugs, e.g. sulfinpyrazone co-prescribed, with 4-weekly serum urate measurement and dose up-titration.
- Monotherapy with uricosuric drugs such as sulfinpyrazone will be utilized if both allopurinol and febuxostat are contraindicated or not-tolerated.
- Once the treatment target is reached (i.e. serum urate < 360 µmol/L), the practice-staff will confirm with the participant that this was at least two weeks clear of the previous gout flare. For participants experiencing a gout flare in this period, the serum urate will be measured at least 2 weeks from the date of self-reported resolution of the gout flare. If the serum urate is ≥360 µmol/L at this point, the dose of ULT will be increased as outlined above.
- Once serum urate is <360µmol/L, ULT prescription will occur 2-monthly without any face-to-face visits. Four-weekly serum urate measurements will stop once the serum urate level is <360µmol/L.
- Participants will have serum urate measured at year 1 and year 2 research assessment visits (see later page 42). The practice-staff of participants randomized to the intervention arm will be made aware of the results of these tests. They will inform the study participants, and those no longer achieving treatment target will be reviewed to discuss adherence with ULT. Participants adherent to ULT will have the dose of ULT increased where possible using treat to target strategy outlined above.
- Participants can request further clinical visits, or telephone advice from the practice nurse, for their gout, as needed.
- The lead applicant, and two of the clinical co-investigators (ER, MS with CDM and PL deputizing in case of leave) will advise the practice nurse and the GP signing the prescription if required.

[figure not shown]
Page 38 of 71 Treat to target in gout Protocol Final Version 1.1 date 29 May 2019

• Each participating GP surgery will have a nominated GP for signing the ULT prescription, and the research trained practice nurses will not treat control arm gout patients for the study duration. The practice nurse will be required to not disseminate their experience with ULT to other staff members during the study.

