7.11 Criteria for terminating the trial

The trial will be stopped if:

[1] on an interim analysis there are overwhelming and undoubtable evidence of efficacy and/or major safety concerns,

[2] relevant new information become available, or

- [3] there are or issues with trial conduct such as
 - (a) poor recruitment,
 - (b) loss of resources.

The trial may be discontinued in one region if there is:

[1] poor recruitment, or

[2] poor adherence to the protocol.

The decision to terminate the trial in a single region or in all regions will be made after review by the TSC/DMC.

If this were to occur, all unused trial supplies e.g. medicines will be returned to the local NHS Pharmacies by the study participants for disposal as per usual NHS practice.

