8.2 Internal Pilot

Analytical plan: Baseline categorical outcomes will be summarized using frequencies and percentages, and continuous outcomes will be summarized using means (standard deviations) and medians (interquartile range). Particular attention will be paid to missing items and patterns of missing data from the electronic capture of gout flare severity and QoL. No formal statistical comparisons between treatment arms will be made, but 95% CIs will be calculated for [1] the between-group difference in the gout flares count, between months 7– 12 in the two arms, and [2] the proportion meeting serum urate treatment target, and the between-group difference in these proportions, at month 12. Adherence with ULT will be assessed in the experimental and control arms (for control-arm participants who are on ULT using the MPR, taking the returned pill count into account, with a MPR \geq 80% or MMAS-8 >6 defined as being adherent [53]).

Signal of efficacy outcome measure and time-point: It is difficult to determine signal of efficacy from pilot studies. This is especially true for gout, where flares become more frequent in the first few months of initiating ULT, and continue for 6 months to 1 year (or even longer) after starting treatment. This is a direct effect of urate-lowering, which causes crystal dissolution, encouraging shedding of crystals in to the joint space which triggers a flare. In fact, gout treatment guidelines recommend flare prophylaxis (e.g. colchicine) for at least 6 months after starting ULT. In keeping with these, all study participants will be prescribed flare prophylaxis for 6 months in this study. Thus, we cannot use the number of flares in the first 6 months of ULT to gain a preliminary signal of efficacy. We will therefore estimate the number of gout flares in months 7–12 between the two arms. However, this does not form part of the thresholds to progress to the main trial (see below).

Threshold for progressing to the main trial: Page 48 of 71

Treat to target in gout Protocol Final Version 1.1 date 29 May 2019

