8.5 Long term follow-up

The data analysis in this phase will be conducted on the same lines as described in the RCT. Death, and incidence or progression of CKD, myocardial infarction, ischaemic heart disease, stroke will be analysed using a time-to-event survival model. ULT prescription will be included as a time-varying covariate in this analysis. A multivariable linear model will be used to compare healthcare utilization between the groups.

Interim analyses will inform efficacy and trial management. These results will be available to the main analysis team, and the outcome of these analyses may affect the conduct of the study. Unless other interim analyses are requested by the DMC, only one interim analysis is planned, at the end of the internal pilot.

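### The TMG and TSC are declared blind until the main analyses, yet they receive by-arm pilot results, so their blinding to arm-level results cannot last beyond the pilot

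*Protocol*

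**What the plan says.** **Declared blinding.** Protocol 6.4.1 states: "The trial management group and the TSC will be blind to group allocation; none of these individuals will have contact with study participants". It adds: "Unblinding to the study team will only occur once the main trial analyses have been completed". The same section exempts the statistician, because the urate differences will show which arm is which.

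**Release of interim results.** Protocol 6.4.2 plans one interim analysis, at the end of the internal pilot, and says: "The results of the interim analysis at this time-point will be available to the trial management group (TMG), TSC, and DMC". Section 8.5 says of interim results: "These results will be available to the main analysis team, and the outcome of these analyses may affect the conduct of the study".

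**What those results contain.** Section 8.2 says: "No formal statistical comparisons between treatment arms will be made". It nevertheless asks for 95% confidence intervals for "the between-group difference in the gout flares count" over months 7-12 and for the between-arm difference in the proportion at urate target at month 12. One feasibility criterion is the proportion at target in the named intervention arm. Flares in months 7-12 are excluded from the progression thresholds, but are to be shown to the TSC and the HTA Board.

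**Related text.** Section 7.1 says that the lead applicant and clinical co-investigators "will advise the practice nurse and the GP signing the prescription if required". Section 7.11 lets the trial stop if "on an interim analysis there are overwhelming and undoubtable evidence of efficacy".

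**The concern.** The people declared blind are the people given the comparison. The pilot is the first 90 participants of the main trial, and months 7-12 lie inside the 24-month primary outcome window, so the released figure is an early look at part of the primary result in participants who will be in the final analysis.

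The same bodies keep discretion after seeing it. Under 8.1 the TMG, TSC and DMC approve the SAP, which has to be final only before the data are unblinded. Once by-arm pilot results have been circulated, it is unclear when that moment is. Under 8.1 the TSC also approves deviations from the SAP. Under 8.2 the method of collecting the primary outcome may change after the pilot, and under 8.5 the interim may affect conduct. In an open-label trial with participant-reported flares, the blinding of those who make such decisions is one of the few protections left, and the final report would claim it for the whole trial.

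**Working it through.** **1. The sections side by side.**

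| Question | Section | What it states |
|---|---|---|
| Who is blind? | 6.4.1 | TMG and TSC, to group allocation |
| Until when? | 6.4.1 | Study team: until the main analyses are complete |
| Who receives the pilot interim? | 6.4.2 | TMG, TSC and DMC |
| Who receives the pilot flare data? | 8.2 | TSC and HTA Board |
| Is it comparative? | 8.2 | Yes: between-arm differences in flares and in urate target |
| Is an arm named? | 8.2 | Yes: the urate criterion applies to the intervention arm |

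The first two rows cannot both hold with the last four, if blinding covers arm-level results. The protocol's own usage suggests that it does: 6.4.2 has the TMG and TSC review serious adverse events by blinded group and keeps unblinded safety data for the DMC.

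**2. Would coded labels (A/B) preserve the blind?** Let X be the number at target in the intervention arm and Y in the control arm, each binomial with n per arm. The probability that the arm with more participants at target is the intervention arm is P(X > Y) = Σ P(X = i) · P(Y < i).

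Inputs: n = 45 per arm (90/2), or 36 after 20% attrition. The intervention proportion is 70% or 50% (the thresholds in 8.2) or 95% (the earlier nurse-led trial at year 2, section 3). The control proportion is 30%, which is that trial's year 2 figure and is assumed here for month 12.

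| Intervention v control | 45 per arm | 36 per arm |
|---|---|---|
| 95% v 30% | above 0.9999 | above 0.9999 |
| 70% v 30% | 0.9999 | 0.9997 |
| 50% v 30% | 0.968 | 0.949 |

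Coding fails even at the lower threshold. This agrees with the reason that 6.4.1 gives for not blinding the statistician.

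**3. What would be lost by withholding the flare comparison?** Its precision is

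SE(log RR) = √{[(1/m₀ + k) + (1/m₁ + k)]/n}.

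Inputs: k = 1.5 and the 24-month control mean of 3.54, both from 8.6. With an even flare rate, m₀ = 3.54/4 = 0.885 over six months. With a rate ratio of 0.65, m₁ = 0.65 × 0.885 = 0.575. Retention is taken as complete, n = 45.

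- SE = √{[(1.130 + 1.5) + (1.738 + 1.5)]/45} = √(5.868/45) = 0.361
- 95% CI = 0.65 × exp(±1.96 × 0.361) = **0.32 to 1.32**

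Two variations:

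- 36 per arm: SE = √(5.868/36) = 0.404, CI 0.29 to 1.43.
- The earlier trial's usual-care mean of 3.5 in year 1 (section 3), so m₀ = 1.75, m₁ = 1.1375, n = 45: SE = √{[(0.571 + 1.5) + (0.879 + 1.5)]/45} = 0.314, CI 0.35 to 1.20.

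At the design effect the interval includes 1 each time.

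**4. Share of the trial exposed.** 90/466 = 19%.

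**The case against.** The best defence is that 6.4.1 promises blinding to allocation, and that aggregate results disclose nobody's allocation. That is right as far as it goes. A reader might infer that the stated blinding does not exist at all, and the text does not support this: individual allocation can stay hidden from the TSC, by-arm data gathered after the pilot can stay masked, and adverse event review is still described as blinded. What the defence does not rescue is blinding to arm-level results.

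Other inferences also go too far:

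- **Advising clinicians.** A reader might take those named in 7.1 to be TMG members. Section 6.5 says that the chief investigator and co-investigators manage the study, but no membership list is given. Advising a nurse or GP is not contact with participants, although it can reveal the allocation of the participant discussed.
- **Release to the analysis team (8.5).** This is consistent with 6.4.1, which says openly that the statistician is not blind.
- **Stopping for efficacy.** Section 7.11 speaks of an interim analysis in general, 8.5 allows others at the DMC's request, and 6.5 places stopping guidelines in a DMC charter that is not at hand. It is not shown that the pilot comparison would serve as a stopping rule. The wording does leave the question open, because the pilot interim is the only one planned.
- **Serious adverse event causality.** The protocol never claims that this is assessed blind, so there is no contradiction there.

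Finally, participants, GPs and the statistician already know the allocation, and flares are classified by a fixed definition. No direct path from TMG or TSC knowledge to a flare count is shown. The exposure is through decisions on conduct and analysis, and its size cannot be calculated from the document.

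**Conclusion.** The contradiction between 6.4.1 and sections 6.4.2 and 8.2 is real. The TMG and TSC cannot remain blind to arm-level results once the pilot is reported, and coded labels would not change that. What is exposed is an early comparison of part of the primary outcome in 19% of the planned sample, seen by bodies that still approve the SAP and its deviations and can alter conduct. The conclusion rests on reading the declared blinding as covering arm-level results, as the handling of adverse events in 6.4.2 suggests. The identification probabilities assume 30% of controls at target at month 12. The claim extends neither to disclosure of individual allocation nor to any demonstrated bias in the flare counts. It should be corrected, and the correction is mainly one of wording.

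**What to change.** 1. Amend 6.4.2, 8.2 and 8.5 so that the by-arm flare comparison at the pilot goes to the DMC only.
2. Give the TMG, TSC and funder pooled consent, attrition and diary completeness, plus the intervention-arm urate and adherence results that the progression rule needs. A met or not-met statement against each threshold would disclose less and would also suffice.
3. In 8.1, require the SAP to be final before the by-arm pilot comparison is produced.
4. Restate 6.4.1 to say what the TMG and TSC are blind to and until when, and that investigators who advise under 7.1 may know the allocation of the participants discussed.
5. Reconcile 7.11 and 8.5, where an interim informs efficacy and may lead to stopping, with 8.2, where there is no formal comparison and flares are not a progression criterion. State whether the pilot interim has any efficacy-stopping role.

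The cost is amended protocol wording, matching DMC charter text and an earlier SAP deadline. The TMG, TSC and funder lose sight of a comparison that no progression criterion uses and that is too imprecise at this size to guide them.

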6.5 TRIAL/STUDY MANAGEMENT

The study will be managed by the chief investigator, in collaboration with the co-investigators and the Keele CTU. An independent DMC and a TSC will be constituted. The DMC and TSC will have a named chair, and members with statistical, clinical trial, and clinical rheumatology and primary-care expertise.

TRIAL STEERING COMMITTEE

The role of the TSC will be to provide overall supervision for the project on behalf of the Sponsor and Funder and to ensure that the project is conducted to the rigorous standards set out in the Department of Health's Research Governance Framework for Health and Social Care and the Guidelines for Good Clinical Practice.

The main responsibilities of the TSC will be as follows:

- To provide advice, through its Chair, to the Funder, the Sponsor, the Chief Investigator, the Host Institution and the Contractor on all appropriate aspects of the trial
- To monitor progress of the trial, adherence to the protocol, patient safety (where appropriate) and the consideration of new information of relevance to the research question
- Safeguard the rights, safety and well-being of the participants
- To ensure appropriate ethical and other approvals are obtained in line with the project plan
- To agree proposals for substantial protocol amendments and provide advice to the Sponsor and Funder regarding approvals of such amendments
- To provide advice to the investigators on all aspects of the trial.

The TSC members will be contracted by the Sponsor using the Sponsor's standard TSC contract and charter which will detail the constitution and composition of the TSC.

The responsibility for calling and organizing TSC meetings lies with the Chief Investigator, in association with the Chair. There may be occasions when the Sponsor or the Funder will wish to organize and administer these meetings. This is unlikely, but the NIHR reserves the right to attend any meeting, and should therefore should be included in relevant invitations, and also reserves the right to convene a meeting of the TSC/SSC in exceptional circumstances.

Page 31 of 71 Treat to target in gout Protocol Final Version 1.1 date 29 May 2019

The Role of the Chair of the TSC:

The Chair of the TSC is directly answerable to the relevant NIHR programme, as funder. The Chair's responsibilities are also detailed in the Sponsor's TSC contract and charter.

DATA MONITORING COMMITTEE

The role of the DMC is as follows:

- To monitor trial data and make recommendations to the TSC on whether there are any ethical or safety reasons why the trial should not continue
- The safety, rights and well-being of the trial participants are paramount
- The DMC considers the need for any interim analysis advising the TSC regarding the release of data and/or information
- The DMC may be asked by the TSC, Sponsor or Funder to consider data emerging from other related studies
- There are also rare occasions when the DMC chair might be asked by the Funder to provide a confidential interim or futility analysis if serious concerns are raised about the viability of the study or if the research team are requesting significant extensions.

The standard Sponsor DMC contract and Charter will be prepared containing details of membership, terms and conditions and full details of stopping guidelines. The DMC will report their assessment to the independent chair of the TSC.

The Chief Investigator has overall responsibility for the study and shall oversee all study management.

The data custodian will be the Chief Investigator. The Chief Investigator will delegate the data custodianship to the CTU Lead Statistician for the period of the trial, defined as the period up until the publication of the main trial results The CTU shall collect, hold and analyse the Data during the course of the Project in accordance with the Protocol.

Following the publication of the main results of the randomised controlled trial (RCT), the Data shall be transferred to Nottingham in encrypted format, along with any information needed to de-encrypt the Data, for final archiving.

6.5.1 Trial Data Sharing

During the trial any data access requests will be agreed with the Chief Investigator. No work based on the data shared under a data access request should be submitted for publication or included in presentations until the outcome of the main trial has been published in accordance with the terms of the funder and the collaboration agreement.

After the trial data transfer to the University of Nottingham, any future internal or external data requests will be handled by the University of Nottingham, who will keep the CTU informed about the number and outcomes of such requests. The Chief Investigator may be supported in handling these requests by the CTU Lead Statistician for the duration of their involvement with the trial.

Page 32 of 71 Treat to target in gout Protocol Final Version 1.1 date 29 May 2019

6.6 DURATION OF THE TRIAL / STUDY AND PARTICIPANT INVOLVEMENT

Study Duration: 80 months. Enrolment begins: month 4 Last visit of last participant in trial: month 56 End of study: month 80

Participant Duration: 2 years, with further 2 years' follow up after the last study visit.

End of the Trial

The end of the trial will be the point at which all long-term follow-up data has been received and cleaned for analysis.

6.7 SELECTION AND WITHDRAWAL OF PARTICIPANTS

6.7.1 Recruitment

Trial setting: Primary care.

Recruitment: Primary care and community-based recruitment.

- A. GP surgery lists
- Practice staff will search the GP records electronically to identify people with gout based on either any previous diagnosis, previous colchicine prescription, or current or previous ULT prescription.
- The GP will review the patient list to exclude potentially unsuitable participants. e.g. those with dementia, terminal cancer, and severe enduring mental illness.
- Potential study participants will be posted a covering letter, a participant information sheet (PIS), brief questionnaire to (a) assess eligibility, (b) enquire about willingness to participate in the study and for further contact by the research team to arrange for a screening research visit, (c) enquire about contact details, and a freepost envelope addressed to Keele CTU, by the GP surgery staff.
- In case of non-response after 4 weeks, the GP surgery will send a reminder letter to the participant enclosing the PIS and brief questionnaire.
- B. Local community advertising:

In order to recruit participants who may not have consulted their local GP about gout, we will:

- Put up study posters in participating GP surgeries or local pharmacies to inform people with gout who may not have been identified in GP electronic medical record search,
- Put up study posters in up to ten local community centers in each region, and
- Advertise the study in local newspapers.

The posters and advertisements will signpost people interested in participating in the study to

Page 33 of 71 Treat to target in gout Protocol Final Version 1.1 date 29 May 2019

contact Keele CTU. Keele CTU will then contact them as described above.

Initial screening for eligibility:

- Keele CTU will assess eligibility based on questionnaire responses.
- Details of potentially eligible participants will be passed to the regional trial staff in the East Midlands, West Midlands, and Wessex, based in Nottingham, Keele and Southampton Universities respectively with participant consent and the appropriate data transfer agreements.
- It will be explained to the study participants that their identifiable details will be passed by the Keele CTU to the regional trial staff Nottingham, Keele and Southampton Universities respectively.
- Staff in the Keele CTU and regional trial staff will arrange for the potential participants to be invited for a screening visit at their GP surgery. Screening visits can also be arranged at the participants' own homes if they are unable to attend the GP surgery due to other commitments, e.g. due to work.

Screening visit: The screening visit will be conducted by the regional trial staff. At the screening visit written informed consent will be obtained, participants' eligibility for participation in the trial will be assessed (see section below), and for those potentially eligible based on verbal enquiry, blood will be collected for measuring serum urate, urea and creatinine.

As serum urate can reduce during a gout flare, care will be taken to schedule screening visits at least 2 weeks after self-reported resolution of the gout flare.

Participants who do not meet the eligibility criteria at the screening visit will be informed and the reason(s) for this will be explained. Similarly, participants who give blood for serum urate and creatinine measurement, and have a serum urate level < 360μ mol/L, or eGFR < 30μ m/min will be explained that they do not meet the eligibility criteria for participating in this study. They will be thanked for their time and contribution and advised to consult their GP for gout flares as usual. It will be explained to them that their data collected so far will be used anonymously in the analysis. Screen failures will be replaced with other participants willing to take part in the study.

It will be explained to potential participants that entry into the trial is entirely voluntary and that their treatment and care will not be affected by their decision. It will also be explained that they can withdraw at any time without having to provide a reason. In the event of their withdrawal it will be explained that their data collected so far cannot be erased and we will seek consent to use the data in the final analyses where appropriate.

